8.4. Packaging and Labeling

The label(s) for IP will include sponsor name, address and telephone number, the protocol number, IP name, dosage form and strength (where applicable), amount of IP per container, lot number, expiry date (where applicable), medication identification/kit number, dosing instructions, storage conditions, and required caution statements and/or regulatory statements as applicable. Additional information may be included on the label as applicable per local regulations.

No blinding is applied in this study.

8.5. Clinical Supplies

The investigator(s) or designee(s) is responsible for taking an inventory of each shipment of IP received and comparing it with the accompanying shipping order form. The investigator(s) or designee(s) will verify the accuracy of the information on the form and call the IRTS to register the IP received at the site.

At the study site, all IP will be stored according to the storage conditions described on the IP packaging label in a locked, safe area to prevent unauthorized access. The IP must be stored as directed on the package label at a controlled temperature, and a temperature log must be maintained in the source documents.

8.6. Investigational Product Accountability and Disposal

Investigational product accountability will be assessed by the investigator or designee. Applicable information such as lot number, tablet or vial count, and expiration date should be collected, as well as information provided by the subject or the caregiver (eg, subject dosing diary).

Investigational product accountability should be assessed before drug dispensing for each subsequent treatment cycle in the treatment phase, starting on Day 1 of Cycle 2, and at the treatment discontinuation visit.

The investigator(s) or designee(s) is responsible for accounting for all IP that is issued and returned by the subject during the course of the study according to applicable regulatory requirements. Any unused IP must be returned by a study subject and retained by the investigative site for accountability to be conducted by a Celgene representative (or designee). If any IP is lost or damaged, its disposition should be documented. At periodic monitoring visits, a Celgene representative (or designee) will conduct IP accountability and address any discrepancies. Upon satisfactory reconciliation of all IP, returned IP may be destroyed. At the conclusion of the study, all remaining IP will be counted, reconciled with dispensing records, documented, and destroyed at the clinic site or allocated drug destruction location after completion of drug accountability by a Celgene representative (or designee). The Celgene representative (or designee) will ensure that a final report of drug accountability to the unit dose level (ie, tablet) be prepared and placed in both the investigator study file and the central clinical study file.

A copy of the site's Standard Operating Procedure (SOP) for drug destruction may be collected by the sponsor (or designee). Any revisions to a site's destruction process must be provided and

approved by the sponsor (or designee) prior to implementation of this protocol. Any site without a sponsor (or designee)-approved destruction SOP and process will be required to return IP to Celgene. Celgene (or designee) will review with the investigator and relevant site personnel the process for Investigational Product return, disposal, and/or destruction including responsibilities for the site versus Celgene (or designee).

8.7. Investigational Product Compliance

Subjects will self-administer CC-486 doses in the treatment phase. Durvalumab will be administered at the study site. Documentation of dosing during treatment will be recorded in a study-specific diary card. Investigational product administration diary cards will be provided by the sponsor to study site personnel, who will in turn distribute them to study subjects. Study site personnel will enter the scheduled daily doses, the number of tablets to be taken each day, and any other applicable information. Study site personnel will review the dosing information with the subject (or legally authorized representative) on scheduled clinic visit days. Subjects (or legally authorized representative) will be asked to record IP dosing information in the diary card and to bring the diary card and unused tablets in the blister card (or the blister card packaging even if it is empty) with them to scheduled clinic visits (ie, prior to the start of the next treatment cycle). A diary card and tablet compliance check will be performed by study personnel. Diary cards must be saved and kept with the source documentation. Study site personnel will perform an IP administration compliance check and record this information in the subject's source documentation and on the appropriate CRF.

Administration of all IP will be recorded, including dispensing, dosing, and any changes in dosage administration such as interruption or reduction in dosing due to an AE.

9. CONCOMITANT MEDICATIONS AND PROCEDURES

All prior and concomitant medications (prescription and non-prescription), treatments, and therapies taken from 28 days (4 weeks) prior to the first dose of IP, up to 28 days after the last dose of CC-486 (90 days for durvalumab), or up to the last study visit, whichever date is later, must be recorded on the appropriate CRF.

All prior treatments for MDS, including ESAs, thrombopoiesis-stimulating agents (TSAs), iron-chelating agents, chemotherapy, cytotoxic therapy, investigational agents, or other medications considered supportive care for MDS should be recorded on the respective CRF(s) regardless of discontinuation date of treatment.

Concomitant medications should be kept to a minimum during the study. However, if considered necessary for the subject's welfare and are unlikely to interfere with the IP, they may be given at the discretion of the investigator.

9.1. Permitted Concomitant Medications and Procedures

Best supportive care may be used in combination with study therapy if deemed necessary. Best supportive care for this study includes, but is not limited to, treatment with RBC or whole blood transfusions, fresh frozen plasma transfusions, single donor or pooled donor platelet transfusions, antibiotic, antiviral and/or antifungal therapy, nutritional support as needed, and myeloid growth factors (G-CSF and GM-CSF) for subjects experiencing neutropenic infections. The use of myeloid growth factors is also allowed for secondary prophylaxis under certain conditions as described below. The use of these products will be considered as concomitant treatment and documented as concomitant medications, therapies or procedures.

Blood product support (RBCs and platelets) may be administered according to institutional standards. RBC and platelet transfusions will be considered concomitant procedures and should be collected on the appropriate CRF.

Subjects who are currently using iron-chelating agents should be on a stable or decreasing dose for at least 8 weeks (56 days) prior to enrollment. Initiation, modification, and/or discontinuation of iron-chelating agents during the treatment phase of the study is discouraged and should be discussed with the medical monitor first whenever possible.

Subjects may be administered supportive and palliative care (eg, pain control) as clinically indicated throughout the study.

It is recommended that an antiemetic medication such as a serotonin 5-HT₃ receptor antagonist (eg, ondansetron) be taken 30 minutes prior to IP administration during Cycle 1 of the treatment phase. If nausea/vomiting is not significant, further antiemetic prophylaxis may not be needed. Pre-treatment or post-treatment with a serotonin 5-HT₃ receptor antagonists, or other locally available and appropriate antiemetic medication, will be considered concomitant treatment and should be recorded on the appropriate CRF.

Treatment with antidiarrheal medications is recommended at the first sign of diarrhea as per the guidelines in [Appendix H](#). Pre-medication with antidiarrheal medication for subsequent doses of CC-486 and/or durvalumab may be appropriate. Pre- and post-treatment with an antidiarrheal must be recorded in the CRF as concomitant medication.

Myeloid growth factors (G-CSF and GM-CSF) may be given per investigator's discretion for the treatment of neutropenic fever/infections as well as for secondary prophylaxis if the subject had a previous event of neutropenic fever/infection or neutropenia Grade 4 during the treatment phase of the study and the safety of the subject is considered jeopardized by subsequent episodes of neutropenic fever/infections or Grade 4 neutropenia.

For subjects who develop an ANC $< 0.5 \times 10^9/L$ (or per institutional standards), administration of prophylactic fluoroquinolone antibiotics (eg, ciprofloxacin or levofloxacin) or other recognized prophylactic antibiotics may be considered and documented as a concomitant medication on the appropriate CRF. If neutropenic fever/infection occurs, treatment should consist of a broad spectrum antibiotic, and if the investigator deems the use of a myeloid growth factor to be medically important, myeloid growth factors may also be administered. For secondary prophylaxis with myeloid growth factors, the dose modification guidelines detailed in Section 8.2.4 remain applicable. Discontinuation of secondary prophylaxis with myeloid growth factors should be considered by the investigator as clinically appropriate.

Concurrent systemic corticosteroids for medical conditions other than MDS are allowed, provided the subject is on a stable or decreasing dose for ≥ 1 week prior to the first dose of IP. Initiation, modification, and/or discontinuation of corticosteroids during the treatment phase of the study is discouraged and should be discussed with the medical monitor first whenever possible.

9.2. Prohibited Concomitant Medications and Procedures

Best supportive care for this study specifically excludes cancer surgery, immunotherapy, biologic therapy, radiotherapy, anticancer hormonal therapy, and systemic chemotherapy where the goal is to eradicate or slow the progression of the disease.

The following concomitant medications are specifically **prohibited** during the course of the study:

- Cytotoxic, chemotherapeutic, targeted, or investigational agents/therapies
- Azacitidine for injection, decitabine, or other demethylating agents
- Lenalidomide, thalidomide, and other immunomodulatory drugs (IMiDs)
- Erythropoiesis stimulating agents and other hematopoietic growth factors (eg, interleukin-3)
- Romiplostim and other TSAs (eg, Interleukin-11, Eltrombopag)
- Hydroxyurea
- Androgens, unless to treat hypogonadism
- Oral retinoids (topical retinoids are permitted)
- Arsenic trioxide
- Interferon
- Immunosuppressive medications including, but not limited to systemic corticosteroids at doses exceeding 10 mg/day of prednisone or equivalent, methotrexate,

azathioprine, and TNF- α blockers. Use of immunosuppressive medications for the management of investigational product-related AEs or in subjects with contrast allergies is acceptable. In addition, use of inhaled, topical, intranasal corticosteroids or local steroid injections (eg, intra-articular injection) is permitted. Temporary uses of corticosteroids for concurrent illnesses (eg, food allergies, CT scan contrast hypersensitivity, moderate to severe infusion-related reactions, etc.) are acceptable upon discussion and agreement with the medical monitor.

- Live attenuated vaccines during the study through 30 days after the last dose of durvalumab.

Refer to Section 7.3 for exclusion criteria pertaining to prohibited concomitant medications.

9.3. Required Concomitant Medications and Procedures

There are no required concomitant medications, although prophylactic treatment with an antiemetic or antidiarrheal medication may be considered and is recommended during the first cycle of treatment.

10. STATISTICAL ANALYSES

The sections below provide an overview of the proposed statistical considerations and analyses.

10.1. Overview

This is an open-label, randomized 2-arm study to estimate the efficacy of CC-486 as a monotherapy and CC-486 + durvalumab as a combination therapy in subjects with MDS who fail to achieve an objective response to treatment with azacitidine for injection or decitabine.

The study consists of 5 phases: *Screening, Safety Run-in, Randomized Treatment, Follow-up, and Extension*. The randomized treatment phase will be conducted in 2 stages, with a futility assessment planned at the completion of Stage 1 to determine whether the null hypothesis ($H_0: p < 12.5\%$) can be rejected with 3 or more responses in Stage 1. If 3 or more responses have been observed before the end of Stage 1, the planned futility assessment may be performed earlier than at the completion of Stage 1 to confirm the finding of responses. This earlier analysis will replace the futility analysis planned at the completion of Stage 1. This earlier futility assessment will have the same integrity as the futility assessment planned at the completion of Stage 1. An analysis will be performed at the completion of Stage 2 to estimate the overall response rate of treatment of all the subjects in the cohort.

The primary objective is to evaluate the treatment response with CC-486 monotherapy and combination therapy in this sample of subjects. The secondary objectives include the evaluation of overall survival, time to response, duration of responses, time to disease progression, and safety and tolerability of the regimen in this population.

This section defines the subject populations for various statistical data analyses, the justifications of sample sizes for the cohorts, and the methodologies that will be used for the efficacy and safety analyses. All statistical analyses specified in this protocol will be conducted using SAS® Version 9.2 or higher unless otherwise specified.

10.2. Study Population Definitions

10.2.1. Intent-to-Treat Population

The intent-to-treat population will include all enrolled subjects who received at least one dose of IP.

10.2.2. Modified Intent-to-Treat Population

The modified intent-to-treat (mITT) population includes all ITT subjects who have at least one post-baseline efficacy assessment performed, met all inclusion/exclusion criteria, and received a minimum of one cycle of treatment.

10.2.3. Safety Population

The safety population will include all enrolled subjects who have received at least 1 dose of IP and had at least 1 post-dose safety assessment.

10.2.4. Evaluable Population

Intent-to-treat subjects who have at least 1 post-baseline efficacy assessment performed, experienced no major protocol deviations during the study, and have received a minimum of 1 cycle of treatment are considered to be in the evaluable population. This definition will be further clarified in the final statistical analysis plan before database lock.

10.2.5. Pharmacokinetic Population

The pharmacokinetic population will include enrolled subjects who have evaluable concentration data to determine the pharmacokinetic parameters from at least one dose of IP.

10.3. Sample Size and Power Considerations

The sample size required will be identical for each treatment arm in each cohort and is estimated using the optimal design of the Simon's two-stage design method (Simon, 1989). The null hypothesis of the response rate will be tested against a one-sided alternative.

For each cohort, the null hypothesis of the response rate ($H_0: p \leq 0.125$) will be tested against the alternative hypothesis of the response rate ($H_1: p \geq 0.27$) with a type I error rate of 10% and 80% power. During the first stage, 16 subjects will be accrued per cohort. If there are 2 or fewer responses in these 16 subjects, the cohort will be stopped and no further recruitment will be needed. Otherwise, 25 additional subjects will be accrued per cohort for a total of 41 subjects in each cohort. If 8 or more responses are observed in these 41 subjects, the null hypothesis will be rejected.

For each cohort, in addition to the evaluation of treatment responses based on objective response criteria, the quality of responses will also be considered for the decision whether to continue the cohort to the second stage of the study. *Quality of response* will be assessed based on the magnitude of hematologic and biologic responses observed in individual subjects, with special consideration for response duration and will be specified with more details in the final Statistical Analysis Plan (SAP).

10.4. Background and Demographic Characteristics

Subjects' age, height, weight, and baseline characteristics will be summarized using descriptive statistics, while gender, race and other categorical variables will be provided using frequency tabulations. Medical history data will be summarized using frequency tabulations by system organ class and preferred term.

10.5. Subject Disposition

Subject disposition (analysis population allocation, entered, discontinued, along with primary reason for discontinuation) will be summarized using frequency and percentage for both treatment and follow-up phases. A summary of subjects enrolled by site will be provided. Protocol deviations will be summarized using frequency tabulations.

10.6. Efficacy Analysis

All efficacy analyses will be performed on the ITT population.

Supportive efficacy analyses will also be performed using the evaluable population.

10.6.1. Primary Efficacy Analysis

The primary assessment of efficacy will be the overall rate of response (defined as CR, PR, or mCR), and HI as determined using the modified IWG 2006 response criteria for MDS (Appendix F). For hematologic response, CR, PR, and mCR will be determined by investigator assessment (with confirmation by central reviewer), while HI will be derived. The percentage of subjects with the other response outcomes of stable disease, failure, relapse after CR or PR, and disease progression will also be presented. Percentages will also be presented separately for CR, PR, mCR, and HI.

The percent of responders will be estimated using 95% confidence intervals for proportions.

Hematologic response (Complete Remission [CR], Partial Remission [PR], Marrow CR [mCR], Stable Disease [SD], Failure, Relapse after CR or PR, and Cytogenetic Response) is defined according to modified IWG 2006 criteria (Appendix F). Subjects will be classified according to their best response achieved during treatment for the response categories of CR, PR, mCR, SD, and failure. Only subjects who achieve CR or PR will be included in the Relapse after CR or PR category. Subjects will be evaluated for cytogenetic response regardless of their response status in other categories. For cytogenetic response, subjects will be classified as having a complete or partial response based on the best response achieved during treatment. Hematologic response will be presented descriptively using counts and percentages.

The response rates at the end of Stage 2 and the associated 95% confidence interval will be estimated for each cohort which completes Stage 2. Similar estimates for Stage 1 will be provided for any cohort which does not continue to Stage 2. The response rates at the end of Stage 2 will be compared between cohorts of SD and PD subjects (if both cohorts finished Stage 2) using the relative risk ratio or other appropriate methods. Specifically, if relative risk method is used, the ratio of response rates for both cohorts and the associated 95% confidence interval will be estimated.

10.6.2. Secondary Efficacy Analyses

10.6.2.1. Overall Survival

Overall survival (OS), time to death from any cause, will be calculated using date of first dose and date of death, or date of last follow-up for censored subjects. Time to death from any cause is defined as the time between first dose and death from any cause. All subjects will be followed until drop-out, death, or study termination. Drop-out may be due to withdrawal of consent from further data collection or loss to follow-up. Subjects who drop-out or are alive at study termination will have their OS times censored at the time of last contact, as appropriate. The OS curve will be estimated using Kaplan-Meier (KM) method.

10.6.2.2. Time to Onset of Response

Time to onset of first response is defined as the time between the date of first IP dose and the earliest date any response (CR, PR, mCR, or HI) is first observed. Subjects who do not achieve any defined response during the treatment period will be censored at the date of treatment discontinuation, disease progression, or death, whichever occurs first. Time to onset of best

response will be defined in a similar manner. Time to onset of first response and best response for the treatment group will be estimated using KM method.

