10.6.2.3. Duration of Response

Duration of hematologic response/improvement will be determined only for subjects who achieve a response on treatment. Duration of hematologic response/improvement is defined as the time from the date response/improvement is first observed until the date the subject has a subsequently documented relapse or disease progression as defined by the modified IWG 2006 criteria. Subjects who maintain hematologic response/improvement through the end of the treatment period will be censored at the date of treatment discontinuation or death, whichever occurs first. Duration of response will be assessed for both first response and best response. Duration of hematologic response/improvement for the treatment group will be estimated using KM method.

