10.2.2. Time to Onset of Response

- Time to onset of first response is defined as the time between the date of first IP dose and the earliest date any response (CR, PR, mCR, or HI) is first observed.
- Subjects who do not achieve any defined response during the treatment period will be censored at the date of treatment discontinuation, disease progression, or death, whichever occurs first.
- Time to onset of best response will be defined in a similar manner.
- Time to onset of first response and best response will be estimated using KM method.

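### The Kaplan-Meier estimate of time to response censors never-responders when they stop treatment, progress or die, so 1-KM overstates the probability of response on treatment

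*Protocol*

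**What the plan says.** Protocol 10.6.2.2 measures time to first response from the first dose to the earliest CR, PR, mCR or HI. A subject with no response during the treatment period "will be censored at the date of treatment discontinuation, disease progression, or death, whichever occurs first". The estimator follows: "Time to onset of first response and best response for the treatment group will be estimated using KM method". SAP 10.2.2 has the same rule ("Subjects who do not achieve any defined response during the treatment period will be censored at the date of treatment discontinuation", with progression and death also listed) and the same estimator: "Time to onset of first response and best response will be estimated using KM method".

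The section names no analysis set, but Protocol 10.6 does: "All efficacy analyses will be performed on the ITT population". Protocol 10.2.1 defines that set: "The intent-to-treat population will include all enrolled subjects who received at least one dose of IP". Duration of response, by contrast, "will be determined only for subjects who achieve a response on treatment" (Protocol 10.6.2.3). Time to response has no such limit, and a censoring rule for non-responders has a purpose only if they are in the analysis.

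Protocol 10.6.1 and SAP 10.1 classify subjects by best response during treatment. Protocol Section 12 lets the investigator keep treating after progression while the subject is still thought to benefit. Neither document names a competing-risk method for this endpoint, and neither says that a median will be reported.

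**The concern.** KM censoring assumes that a censored subject keeps the same future chance of the event as those still at risk. Here response counts only during treatment, so a subject who stops or dies without one has no remaining chance. KM nevertheless passes that subject's weight to those still on treatment, and every later response then produces too large a step.

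There is a second defect. A subject who progresses, stays on treatment and later responds remains at risk through the progression. A subject who progresses and never responds is removed at that date. Membership of the risk set therefore depends on what happens later, which inflates the curve further.

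At stake is a reported secondary endpoint. The study report would hold an ITT response curve ending above the ITT response rate given in the same report. With few responses, one late responder on a depleted risk set can move the curve sharply.

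**Working it through.** **Stated figures.** The plan gives no number for time to response. Its related figures are the Simon design in Protocol 10.3: null rate 0.125, alternative 0.27, stop if 2 or fewer of 16 respond, reject the null with 8 or more of 41, 10% type I error and 80% power. Exact binomial calculation gives a type I error of 0.0995 and power of 0.8011, so the stated values reproduce. None of this uses the time-to-response rule.

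**Direction.** In the ORR each response has weight 1/n. In 1-KM a response at time t has weight S(t-)/Y(t), where S(t-) is the KM estimate just before t and Y(t) is the number at risk. With no earlier censoring this equals 1/n; after any never-responder has been censored it is larger. So 1-KM exceeds the ORR whenever a never-responder is censored before the last response, whatever the rates.

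**Size under constant hazards.** Inputs:
- ORR of 0.125 and 0.27 (Protocol 10.3).
- Horizon T of 6 cycles = 6 × 28/30.4167 = 5.52 months, and of 12 months.
- Median time m to the competing event (stop, progression or death). The documents do not give it; 3-12 months is assumed.

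Let c = ln 2/m. Solve for the response hazard h in h/(h+c) × [1 − exp(−(h+c)T)] = ORR. Then 1-KM = 1 − exp(−hT).

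Example with ORR 0.27, m = 4 and T = 5.52: c = 0.1733 and h = 0.0934. Check: 0.0934/0.2667 × (1 − exp(−1.473)) = 0.350 × 0.771 = 0.270. Then 1-KM = 1 − exp(−0.516) = 0.403, which is 1.49 times the ORR.

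| m (months) | ORR 12.5%, 6 cycles | ORR 27%, 6 cycles | ORR 12.5%, 12 months | ORR 27%, 12 months |
|---|---|---|---|---|
| 3 | 21.6% (1.73×) | 45.0% (1.67×) | 34.0% (2.72×) | 65.2% (2.42×) |
| 4 | 19.1% (1.53×) | 40.3% (1.49×) | 28.2% (2.25×) | 56.4% (2.09×) |
| 6 | 16.7% (1.34×) | 35.7% (1.32×) | 22.5% (1.80×) | 46.6% (1.73×) |
| 12 | 14.5% (1.16×) | 31.2% (1.16×) | 17.1% (1.37×) | 36.5% (1.35×) |

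Protocol 1.4.1 cites a median survival of 4-6 months in higher-risk disease after HMA failure. Taken as the competing median with death alone, that gives 1.32-1.53 times at 6 cycles and 1.73-2.25 times at 12 months. Protocol 7.1 also admits lower-risk disease, where the excess could be smaller.

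**Worked data sets.** Responses fall at scheduled assessments and never-responders leave at exponential quantiles.
- 2/16 (ORR 12.5%), responses after Cycles 2 and 6, m = 4: 1 − (11/12)(5/6) = 23.6%. Across m of 3-9 months, with the second response after Cycle 4 or 6, the range is 15-27%.
- 8/41 (19.5%), responses by Cycle 6, m = 4: 1 − (28/32)(19/21)(13/15) = 31.4%. Across m of 3-9 months: 24-37%.
- 11/41 (26.8%), responses by Cycle 6, m of 3-9 months: 33-49%, so no median.
- 11/41 with responses out to Cycle 12, m = 4: 1 − (29/33)(20/23)(14/16)(8/9)(4/5) = 52.5%. A median of about 11 months appears, although 30 of 41 subjects never respond.

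**Chance that a KM median appears.** In simulation (3,000 runs, m of 3-9 months, several response-time patterns) it was 0-31% for ORR 12.5% with n = 16, and 2-85% for ORR 27% with n = 41.

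**The case against.** The strongest reply is that this is a descriptive secondary endpoint with no test. The ORR is reported separately with its confidence interval, and nothing in the plan tells the reader to take the KM curve as a response rate. That stands as a limit on the consequences. It does not make the estimator right for this endpoint.

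Three stronger readings are tempting, and the documents do not support them.
- **That the curve must rise far above the ORR.** This needs rapid attrition. With 2 responders in 16, 1-KM can reach 39%, but only if 3 of the 16 are still at risk at Cycle 6: 1 − (11/12)(2/3) = 0.389. No document gives such a rate, and the protocol recommends at least 6 cycles of treatment.
- **That the report will carry a false median.** Neither section promises one. The Amendment 4 justification says both monotherapy cohorts missed the Stage 1 minimum, so each had 2 or fewer responses, and a median is unlikely.
- **That SD and PD cohorts would look falsely alike.** This would require PD subjects to fail earlier by a known amount. No failure rates by cohort are given, and the only planned SD/PD comparison is of response rates after both cohorts finish Stage 2.

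**Conclusion.** The concern holds in limited form. The censoring is informative, and 1-KM overstates the cumulative probability of response on treatment; the direction follows from the rule itself. The size, about 1.2-1.7 times the ORR at 6 cycles and 1.35-2.7 times at 12 months, rests on constant hazards and an assumed median of 3-12 months to the competing event. Any finite KM median would be uninterpretable while the ORR is below 50%, since fewer than half of the subjects ever respond. That the endpoint runs over all dosed subjects is inferred from Protocol 10.6 and the contrast with duration of response; the section does not state it. The primary ORR and the two-stage decision are untouched.

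**What to change.** In SAP 10.2.2, and in Protocol 10.6.2.2 if it is amended again, report time to first and best response descriptively among responders: number, median and range.

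If a curve over all subjects is wanted, replace KM with the cumulative incidence of response. The competing events should be treatment discontinuation without response and death without response. Follow-up for response should not end at progression while the subject remains on treatment. Counting progression as a competing event would be wrong here: treatment may continue past it and best response counts throughout treatment, so later responses would be lost and the plateau could fall below the ORR. Only subjects still on treatment without a response at the data cut would be censored. With complete follow-up the plateau then equals the on-treatment ORR.

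The cost is SAP wording and one table or figure program; no new data are needed.
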